6.1 Primary Endpoint

The primary outcome variable is the total number of calories from sugar-sweetened beverages the participant purchased during the shopping task (see also Table 2).

6.2 Secondary Endpoint

Secondary outcomes are listed in Table 2.

6.3 Statistical Methods

Data preparation and balance tests. To prepare the data, we will first examine all scales to ensure adequate internal consistency (i.e., Cronbach's alpha > 0.70), dropping items as needed to improve consistency. If we are unable to achieve adequate internal consistency by dropping items, we may exclude the unreliable scales from analyses (e.g., not analyze treatment effects on these outcomes).

Next, we will conduct balance tests. Specifically, we will report participants' age, gender, sexual orientation, Hispanic ethnicity, race, educational attainment, health literacy, household income, usual sugar-sweetened beverage consumption, and overweight status (body mass index [BMI] ≥ 25 kg/m²) by trial arm. We will summarize categorical variables as counts and percentages and continuous variables as means and standard deviations. The denominator for each percentage will be the number of participants within each treatment group, less any participants with missing data on the variable of interest. We will use *t*-tests and χ^2 tests to examine whether participants assigned to the trial arms differ on any continuous or categorical characteristics, respectively. We will report *p* values from these balance tests. Subsequent analyses will control for any unbalanced characteristics.

Analysis of the primary outcome (Efficacy analysis). We will use ordinary least squares regression (OLS) to examine whether the primary outcome differs by trial arm. Specifically, we will fit the following:

$$SSB \text{ calories purchased} = \beta_0 + \beta_1 \text{WARNING} + X\beta \quad (\text{Eq. 1})$$

Here, *SSB calories purchased* is the total calories from SSBs the participant had in her basket when she completed her shopping task, calculated as described in Table 2. WARNING is an indicator variable for whether the participant was in the health warning arm (WARNING = 1) or the control arm (WARNING = 0). We denote *X* as a vector of any participant characteristics (e.g., age, gender, race/ethnicity) found to be unbalanced across trial arms in balance tests.

The coefficient on WARNING (β_1) is the primary effect estimate, and gives the average difference in (adjusted) means between the treatment arm and the control arm. It is interpreted as the impact of SSB health warnings on total calories of SSBs purchased.

Planned exploratory analyses of the primary outcome. We will examine whether the following participant characteristics moderate (modify) the effect of SSB health warnings on SSB purchases:

- a) Age category (18-29, 30-39, 40-54, and 55 years or older);
- b) Sex (male vs. female);
- c) Sexual orientation (gay, lesbian, or bisexual vs. not);
- d) Race/ethnicity (white vs. non-white);
- e) Low educational attainment (some college or less vs. college or more),
- f) Limited health literacy (possibility or high likelihood of limited literacy vs. adequate literacy, based on score on the Newest Vital Sign^{63,64});
- g) Household income (\$50,000 or more vs. less than \$50,000);
- h) Usual SSB consumption (above vs. at or below the sample median);
- i) Overweight status ($BMI \geq 25 \text{ kg/m}^2$ vs. $BMI < 25 \text{ kg/m}^2$);

To test whether these characteristics moderate the effect of SSB health warnings on SSB purchases, we will fit a series of regressions (one for each potential moderator) taking the following general form:

$$SSB \text{ calories purchased} = \beta_0 + \beta_1 \text{WARNING} + \beta_2 \text{CHARACTERISTIC} + \beta_3 (\text{WARNING} * \text{CHARACTERISTIC}) + X\beta \quad (\text{Eq. 2})$$

Here, *SSB calories purchased*, *WARNING*, and *X* are as defined previously and *CHARACTERISTIC* is the moderator variable (e.g., an indicator for low educational attainment). Moderation is present if β_3 is statistically significant. We will probe significant interactions by calculating the marginal effect of health warnings on SSB calories purchased at different levels of the moderating variable.

Analysis of the secondary outcomes. We will use different analytic approaches to assess whether secondary outcomes differ by trial arm, depending on the level of measurement of the secondary outcome (i.e., continuous, count, or dichotomous).

The following secondary outcomes are continuous will be assessed using OLS regression:

- Number of calories purchased from all foods and beverages
- Mean intentions to limit consumption of beverages with added sugar
- Mean intentions to limit consumption of specific sugar-sweetened beverages
- Mean attention to trial labels

- Mean emotional reactions to trial labels
- Mean cognitive elaboration
- Social interactions about the labels
- Mean perceptions of added sugar content in specific sugar-sweetened beverages
- Mean attitudes toward consuming specific sugar-sweetened beverages
- Mean product attitudes toward specific sugar-sweetened beverages
- Mean outcome expectations regarding consumption of beverages with added sugar

These regressions will take the general form of:

$$Y = \beta_0 + \beta_1 \text{WARNING} + X\beta \quad (\text{Eq. 3})$$

Here, WARNING and X are as defined previously and Y is the continuous secondary outcome. As above, the effect estimates are given by the coefficient on WARNING (β_1). This coefficient gives the average difference in (adjusted) means between the treatment arm and the control arm; it is interpreted as the impact of SSB health warnings on the secondary outcome being examined.

One of the secondary outcomes, number of SSBs purchased, is a count variable (i.e., takes on only nonnegative integer values) and is thus better evaluated with a count data model. To examine number of SSBs purchased, we will begin by fitting a Poisson regression:

$$\text{Prob}(y|\lambda) = \frac{e^{-\lambda}\lambda^y}{y!} \quad \text{for } y=0,1,2 \quad (\text{Eq. 4})$$

where

$$\lambda = e^{(\beta_1 \text{WARNING} + X\beta)} \quad (\text{Eq. 5})$$

WARNING is an indicator for treatment arm, X is a vector of any unbalanced participant characteristics and y is the observed number of SSBs purchased. Following the advice of Kennedy,⁶⁵ we will use robust standard errors to address the potential for overdispersion. We will test model fit using the Pearson goodness-of-fit test;⁶⁶ if the null hypothesis of a Poisson distribution is rejected, we will use a negative binomial regression in place of a Poisson regression. In either case, we will report the average differential effect of being in the health warning arm (vs. being in the control arm) on the predicted number of SSBs purchased.

Finally, the following secondary outcomes are dichotomous and will be assessed using logistic regression:

- Purchase of a sugar-sweetened beverage
- Noticing of the trial labels

These regressions will take the general form of:

$$Prob(Y = 1|WARNING, X) = \frac{e^{(\beta_1 WARNING + X\beta)}}{1 + e^{(\beta_1 WARNING + X\beta)}} \quad (\text{Eq. 6})$$

WARNING and X are as defined previously, and Y is the dichotomous secondary outcome. For logistic regression results, we will report the average differential effect of being in the health warning arm (vs. being in the control arm) on the probability of the outcome occurring (i.e., probability the participant purchased a sugar-sweetened beverage), calculated using the method of recycled predictions.⁶⁶

Analysis of other outcomes. We will use OLS regression to examine differences by trial arm in the following other outcomes (all of which are continuously measured):

- Mean injunctive norms regarding consumption of beverages with added sugar
- Perceived message effectiveness of trial label
- Support for sugar-sweetened beverage health warning labels
- Mean self-efficacy to limit consumption of beverages with added sugar
- Mean response efficacy of limiting consumption of beverages with added sugar

To examine these outcomes, we will fit linear regressions of the general form:

$$Y = \beta_0 + \beta_1 WARNING + X\beta \quad (\text{Eq. 7})$$

WARNING and X are as defined previously and Y is the continuous other outcome. As above, the effect estimates are given by the coefficient on WARNING (β_1). This coefficient gives the average difference in (adjusted) means between the treatment arm and the control arm; it is interpreted as the impact of SSB health warnings on the outcome being examined.

Statistical software. Data preparation and analyses will be conducted in Stata Version 15.1 (StataCorp LLC, College Station TX).

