| Subject Population key criteria for Inclusion and Exclusion: | 
Inclusion Criteria
 
 1. Age 18 and older 2. Consume at least 1 serving (12 ounces) of sugar-sweetened beverages per week 3. Able to read and write in English 
Exclusion Criteria
 
 1. Under the age of 18 2. Consume less than 1 serving (12 ounces) of sugar-sweetened beverages per week 3. Unable to read and/or write in English |
| Number of Subjects | 400 |
| Study Duration | Each subject's participation will last approximately 30 minutes. The enrollment period is expected to last ~6 months. |
| Study Phases | 
There are two phases:
 
 (1) Screening: screening for eligibility and obtaining consent and (2) Intervention: study intervention/experimental treatment. |
| Efficacy Evaluations | The primary outcome is the total number of calories from sugar-sweetened beverages the participant purchases during the study shopping task, calculated as the sum of calories/container across all sugar-sweetened beverages in the participant's basket at the completion of the shopping task. |
| Statistical and Analytic Plan | 
Primary outcome
 
 • We will use ordinary least squares (OLS) regression to examine whether the primary outcome differs by trial arm, controlling for any participant characteristics found to be unbalanced across trial arms in balance tests. The coefficient on the trial arm indicator variable is the primary effect estimate, and gives the average difference in (adjusted) means between the treatment arm and the control arm. It is interpreted as the impact of SSB health warnings on total calories of sugar-sweetened beverages purchased. 
Secondary outcomes
 
 • We will use OLS regression, logistic regression, and Poisson regression to examine whether continuous, dichotomous, and count secondary outcomes differ by trial arm, respectively. |
| Data and Safety Monitoring Plan | 
 • The principal investigator is responsible for data quality management and ongoing assessment of safety. |

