1 BACKGROUND AND RATIONALE

Obesity, diabetes, and cardiovascular disease are among the leading causes of death in the United States.¹ Consumption of sugar-sweetened beverages (SSBs) such as sodas, fruit drinks, and sports drinks, is a significant contributor to these preventable conditions.²⁻⁶ Despite the health risks of SSB consumption, the average American adult drinks a remarkable 40 to 50 gallons of SSBs every year, accounting for seven percent of daily caloric intake.⁷⁻⁹ To reduce SSB consumption, state and local legislators have proposed requiring SSB containers to bear front-of-package (FOP) labels with health warnings – explicit messages about the health harms of consuming SSBs.¹⁰⁻¹⁵ Despite policymakers’ interest in SSB health warnings, there remain critical gaps in our knowledge of whether and how such warnings change behavior.

Theoretical and empirical work suggest that SSB health warnings are a promising strategy for reducing consumption. Studies of similar textual health warnings on cigarette packs find that warnings reduce smoking in adolescents.¹⁶ Likewise, online randomized trials find that SSB health warnings reduce intentions to purchase SSBs among adolescents,¹⁷ young adults,¹⁸ and parents.¹⁹ In turn, intentions strongly predict behaviors,²⁰ and survey research has shown that intentions to consume SSBs are associated with actual SSB consumption.²¹⁻²³ While this evidence is suggestive, almost no studies have examined whether SSB health warnings change actual behaviors. Answering this question is essential: if effective, SSB health warnings are a highly scalable, low-cost intervention that could reduce SSB intake and chronic disease.

This study aims to evaluate the effects of SSB health warnings on SSB purchases and secondary outcomes using a randomized controlled trial in a naturalistic setting. This Protocol and Statistical Analysis Plan is being submitted as an attachment to the study’s trial registration (NCT #03511937) prior to analysis. The protocol describes the trial objectives, design, and population. The analysis plan pre-specifies planned analyses of the primary, secondary and other outcomes, prior to examining the data. In writing the protocol and statistical analysis plan, we have adhered to the guidelines set forth by Gamble et al.,²⁴ with minor modifications as needed based on trial design.

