4 STUDY PROCEDURES

4.1 Screening Procedures

Eligible participants are English-speaking adults age 18 years or older who consume at least one serving (12 ounces) of SSBs per week. Participants must be willing and able to consent and comply with study procedures. This study does not employ any exclusions based on race, ethnicity, or gender. To determine eligibility, interested participants are asked to complete a brief online survey. The survey queries the prospective participant's age, usual SSB consumption (using an adapted version of the BEV-Q 15, a validated questionnaire⁵⁸), and own and parental educational attainment. Participants aged 18 years or older who consume at least 12 ounces of SSBs per week are invited to schedule a time to participate. Ineligible participants are thanked for their time.

We will track and summarize participant enrollment, allocation, and analysis using a CONSORT diagram. The diagram will report the number of participants who were:

- Assessed for eligibility
- Excluded after screening
 - Excluded because did not meet inclusion criteria
 - Excluded because declined to participate or study visit never scheduled
 - Excluded because cancelled or did not attend study visit
- Randomized
- Received allocated intervention (by treatment arm)
- Analyzed (by treatment arm)
 - Withdrawn and/or excluded from analyses (and reason for exclusion)

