6 STATISTICAL CONSIDERATIONS

General principles and analysis populations. We will use a two-sided critical alpha of 0.05 to conduct all statistical tests. All confidence intervals presented will be 95% and two-sided. Analyses of the primary, secondary, and other outcomes will include all randomized participants according to the trial arm they were randomized to receive. We will use complete case analysis to handle any missing data in analyses of the primary, secondary, and other outcomes.

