6.4 Sample Size and Power

The primary objective of this trial is to evaluate the effect of SSB health warnings on total calories of SSBs purchased. We used G*Power3 to determine sample size needs for

addressing this objective.⁶⁷ At the time of sample size determination, no studies of SSB health warnings had examined behavioral outcomes. Thus, we drew on effect sizes from studies of warnings' impact on intentions to purchase SSBs. These studies report medium^{17,19} or large¹⁸ effect sizes. To account for the intention-behavior gap, we powered the trial to detect an effect size between small and medium (standardized Cohen's $f^2 = 0.02$, i.e., trial arm will explain 2% of the total variance in SSB purchases).⁶⁸⁻⁷⁰ Using these specifications and a two-sided alpha of 0.05, we determined a necessary sample of 395 to detect an effect of $f^2 = 0.02$ or larger with 80% power. To account for potential missing data or incomplete study visits, we aimed to enroll 400 participants (200 in each arm).

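### Balance tests at 0.05 choose the covariates in Eq. 1, so usual SSB consumption, already collected at screening, is left out about 95% of the time and the primary model is not fixed in advance

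*Combined protocol and SAP*

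**What the plan says.** Section 6.3 (Data preparation and balance tests) lists ten characteristics: age, gender, sexual orientation, Hispanic ethnicity, race, education, health literacy, income, usual SSB consumption and overweight status. Each is compared between arms by t-test or chi-square test, after which "Subsequent analyses will control for any unbalanced characteristics". The synopsis gives the same rule for the primary outcome: "controlling for any participant characteristics found to be unbalanced across trial arms in balance tests". X in Eq. 1 is defined by the result of these tests, and the same X is carried into Eqs. 2 to 7. No covariate is always included.

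Section 6.3 sets no threshold of its own for imbalance, so the general statement in Section 6 governs: "We will use a two-sided critical alpha of 0.05 to conduct all statistical tests".

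Section 4.1 shows that the screening survey, completed before any label is seen, records "age, usual SSB consumption (using an adapted version of the BEV-Q 15" and education. Apart from X, usual consumption appears in only one exploratory model, as moderator (h): "Usual SSB consumption (above vs. at or below the sample median".

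Section 1 says of the plan: "The analysis plan pre-specifies planned analyses of the primary, secondary and other outcomes, prior to examining the data".

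**The concern.** A balance test in a randomised trial measures how unusual a chance difference is. It does not measure how well the characteristic predicts the outcome, and only prediction yields precision. The rule can therefore admit a useless covariate and will usually omit a useful one. The plan itself treats usual SSB consumption as relevant: it decides eligibility, is tested for balance and is a planned moderator.

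Three things are at stake.

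- **Precision.** A baseline value already collected is normally not used to reduce the variance of the primary estimate.
- **Pre-specification.** The selection rule is written down, but the covariates in the primary model cannot be named until the arms have been compared.
- **Weak protection against imbalance.** A difference that just misses significance gets no adjustment at all.

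There is also a smaller risk. Section 6.3 expects some missing baseline values, and Section 6 prescribes complete-case analysis. If an incompletely answered item such as income were flagged, those participants would drop out of the primary model. Section 6.4 allows only five spare participants (400 − 395).

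**Working it through.** **Inputs from the documents.** Two-sided alpha 0.05 (Section 6). Effect f² = 0.02, 80% power, N = 395, enrolment 400 at 200 per arm (Section 6.4). Random 1:1 allocation with no stratification described (Section 3.2). Ten characteristics tested (Section 6.3).

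**Assumed input.** The correlation r between usual SSB consumption and SSB calories purchased is not in the documents. The range 0.1 to 0.5 is shown, with r = 0 as the unfavourable case.

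**1. The plan's own figure.** Section 6.4 says "we determined a necessary sample of 395 to detect an effect of" f² = 0.02. With a noncentral F test on one coefficient and λ = f² × N, N = 395 is reproduced exactly. Power is 80.1% at 395 and 80.6% at 400. In standardised units the effect is d = 2√0.02 = 0.283.

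**2. How often covariates enter.** For usual consumption alone the chance is 5% by construction; the simulated rate was 4.9% to 5.2%. If the ten tests are independent, the chance that at least one characteristic enters is 1 − 0.95¹⁰ = 40.1%, so X is empty in 59.9% of trials. If all pairs correlate at 0.3 or 0.5, the chance that at least one enters is about 35% or 29%. Ten in-or-out decisions allow 2¹⁰ = 1,024 possible covariate sets.

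**3. Power and width.** Always adjusting divides the residual variance by its unadjusted value to give 1 − r², so λ = 400 × 0.02/(1 − r²) with 1 and 397 degrees of freedom. At r = 0.3, for example, λ = 8/0.91 = 8.79 and power is 84.1%. The planned rule was simulated with 200 per arm, a normal covariate and outcome, and 60,000 replicates per setting. The Monte Carlo standard error of power is about √(0.8 × 0.2/60,000) = 0.16 points.

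| r | Power, planned rule | Power, always adjust | Mean 95% CI half-width in SD, rule vs always | CI narrower by | Type I error, planned rule |
|---|---|---|---|---|---|
| 0.1 | 80.6% | 80.9% | 0.1965 vs 0.1957 | 0.4% | 4.98% |
| 0.2 | 80.8% | 82.1% | 0.1963 vs 0.1927 | 1.8% | 4.95% |
| 0.3 | 80.9% | 84.1% | 0.1961 vs 0.1877 | 4.3% | 4.90% |
| 0.4 | 81.2% | 86.8% | 0.1958 vs 0.1804 | 7.9% | 4.56% |
| 0.5 | 81.9% | 90.3% | 0.1952 vs 0.1704 | 12.7% | 4.27% |

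The mean estimate under the planned rule was 0.283 at every r, equal to the true value, so there is no bias. In sample-size terms, 400/(1 − r²) means fixed adjustment is worth about 417, 440 and 476 participants at r = 0.2, 0.3 and 0.4.

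**4. Cost if the covariate is useless.** At r = 0, power with 0, 1 or 3 useless covariates is 80.56%, 80.56% and 80.55%.

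**5. Ten candidates instead of one.** Repeating the simulation at r = 0.3 with ten candidate characteristics (6,000 replicates per setting) gave 80.7–80.8% power under the rule and 84.2–84.4% with fixed adjustment. Type I error was 4.8–4.9%.

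**6. Near-miss imbalance.** Suppose the baseline difference has z = 1.9 (p about 0.06), so the rule makes no adjustment. Under the null, the unadjusted test statistic is then approximately normal with mean 1.9r and variance 1 − r². The chance that it exceeds 1.96 in absolute value is 7.7% at r = 0.3 and 9.7% at r = 0.4. Averaged over all allocations the error stays at or below 5%, as in the table.

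**The case against.** The strongest reply is that nothing in the plan's result is wrong. The estimate is unbiased, type I error is not inflated, and N = 395 was computed with no credit for covariates, so the 80% target is met without them. All of that stands.

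The gain also rests on an undocumented r, and there are reasons for caution about high values. The outcome reflects only two beverage picks, so the SSB count is 0, 1 or 2. Eligibility removes everyone below 12 ounces per week, which tends to weaken a correlation. The predictor is self-reported, and the simulation used normal variables. This stands as a limit on how large the benefit may be. It does not favour the planned rule, because adjusting costs nothing measurable even at r = 0.

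A rule with a stated candidate list, stated tests and a stated alpha, blind to outcome, is itself a form of pre-specification. That is right, and the plan does not contradict Section 1. It remains true that the model the rule produces is unknown until the arms are compared.

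No section says outright that the screening answer is carried over to the trial ID. Yet Section 6.3 tabulates usual consumption by arm and uses it as a moderator, so it must be linked to the trial data. Only the source of the value needs to be stated.

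Finally, the computed gain concerns SSB calories only. Extending the covariate to outcomes such as noticing or attention is justified by consistency and lack of harm, not by a demonstrated gain.

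**Conclusion.** The concern holds and should be fixed, as a matter of efficiency and clarity and not of validity. The rule omits usual SSB consumption from Eq. 1 about 95% of the time and leaves the covariate set to chance. The forgone power is about 0.3 points at r = 0.1, 1.3 at 0.2, 3.2 at 0.3, 5.6 at 0.4 and 8.4 at 0.5. It is negligible at the low end and material from about r = 0.3. These figures assume 400 analysed participants, the planned effect f² = 0.02 defined on the unadjusted variance, and a linear relation between approximately normal variables. The 5% entry rate does not depend on r.

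**What to change.** Before the data are examined:

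- Name usual SSB consumption from the screening questionnaire as a fixed covariate in Eq. 1 and in the secondary and other outcome models (Eqs. 3 to 7). Enter it as a continuous variable with a stated transformation. Log ounces per week is one option, and it is defined for everyone because eligibility requires at least 12 ounces.
- If wanted, add screener age and education as further fixed covariates.
- Delete, in Section 6.3 and in the synopsis, the rule that balance-test results decide X. Keep the baseline table as description.
- In Eq. 2, omit the fixed covariate that matches the moderator being tested: usual consumption for (h), and age for (a) and education for (e) if these are used.
- Report the unadjusted difference as a supportive analysis.
- State that the screening value is the one used, and make sure it is in the de-identified dataset before the linking key described in Section 9 is destroyed.

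The cost is SAP wording and one to a few degrees of freedom out of 400. Because eligibility depends on this value, every invited participant should have it, and complete-case analysis should lose nobody on its account. The logistic results are already to be reported as average differences in probability, "calculated using the method of recycled predictions", so adding the covariate does not change what is reported.

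### Nine moderators are each tested at 0.05 and moderation is declared present on significance alone: about a 37% chance of at least one false declaration if the tests are independent and there is no moderation

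*Combined protocol and SAP*

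**What the plan says.** Under the heading "Planned exploratory analyses of the primary outcome", section 6.3 lists nine moderators, lettered a to i; the last is "i) Overweight status". For these, "we will fit a series of regressions (one for each potential moderator) taking the following general form", namely Eq. 2, which has a single warning-by-characteristic coefficient, β3. The decision rule is "Moderation is present if β_3 is statistically significant". The step after it is also tied to significance: "We will probe significant interactions by calculating the marginal effect of health warnings on SSB calories purchased at different levels of the moderating variable".

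The level comes from the general principles in section 6: "We will use a two-sided critical alpha of 0.05 to conduct all statistical tests". The documents give no multiplicity adjustment, global interaction test or ordering for these nine tests. Nor do they say that a significant interaction is only hypothesis-generating.

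Eight moderators are binary. The other is "Age category (18-29, 30-39, 40-54, and 55 years or older". Entered as indicators, this four-level variable needs three interaction coefficients, while Eq. 2 shows one. The plan does not say how age is coded or whether its terms are tested together.

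**The concern.** The heading says exploratory, but the rule under it states a conclusion: a p-value below 0.05 means that moderation exists. Applied nine times, such a rule has a much higher chance of at least one wrong declaration than the 5% a reader may attach to each result.

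The follow-up step adds to this. Marginal effects by subgroup are promised where the interaction was significant, and nothing is said about the rest. Estimates picked out because they crossed a threshold tend to be too large, and more so when power is low. The list includes income, education, race/ethnicity and health literacy. A prespecified finding that moderation is present on one of these could be taken as established when it is a chance result or an exaggerated one.

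**Working it through.** **Inputs.** Two-sided alpha 0.05 for all tests (section 6). Nine moderators, one regression each; age has four levels and the others two (section 6.3). f² = 0.02, 80% power, N = 395, enrolment of 400 at 200 per arm (section 6.4). The documents give no moderator prevalences, no correlations between moderators and no SD for calories. These are therefore assumptions below, and effects are in SD units.

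**1. The plan's own figure.** For one regression coefficient (noncentral F, 1 numerator df, noncentrality f²N), the smallest N with at least 80% power is 395 (power 80.06%; 80.6% at N = 400). The stated sample size reproduces. With equal arms, f² = 0.02 corresponds to d = 2 × √0.02 = 0.283 SD.

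**2. At least one false declaration, independent tests, no true moderation.** 1 − 0.95^9 = 1 − 0.630 = 0.370. The expected number of false declarations is 9 × 0.05 = 0.45, whatever the dependence. The Bonferroni inequality bounds the probability at 45%.

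**3. Correlated moderators and four-level age.** Null trials were simulated: 4,000 per setting, 400 people, 1:1, OLS, calories with many zeros, assumed prevalences of 20% to 50% for the binary moderators, and a common latent correlation.

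| Assumed latent correlation | Age tested jointly on 3 df (nine tests) | Any one of three age terms counts (11 coefficients) |
|---|---|---|
| 0 | 38% | 44% |
| 0.2 | 37% | 43% |
| 0.4 | 36% | 42% |
| 0.6 | 32% | 37% |

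The simulation error is about 0.8 percentage points (√(0.38 × 0.62 / 4000)). For the last column, independence gives 1 − 0.95^11 = 43%.

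**4. Power of one binary interaction.** With a share p in one subgroup, the standard error in SD units is √(4/(400p) + 4/(400(1 − p))).

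- Even split: √(0.02 + 0.02) = 0.20. An interaction of 0.283 SD gives 0.283/0.20 = 1.41 standard errors, so power is about P(Z > 1.96 − 1.41) = 29%. The interaction with 80% power is 2.80 × 0.20 = 0.56 SD. An estimate must exceed 1.96 × 0.20 = 0.39 SD to be significant.
- 10/90 split (illustrative): √(0.100 + 0.011) = 0.33. Power is about 14%, the interaction with 80% power is 0.93 SD, and the smallest significant estimate is about 0.65 SD.

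Even in the favourable case, a significant estimate is at least 0.39 SD. If the true interaction is no larger than the planned main effect of 0.283 SD, every significant estimate in the true direction overstates it.

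**5. What strict control would cost.** At 0.05/9 = 0.0056 per test, the familywise rate is 4.9% under independence and at most 5% under any dependence. The critical value rises to about 2.77. At an even split, power for 0.283 SD falls from about 29% to P(Z > 2.77 − 1.41), about 9%, and the interaction with 80% power rises to (2.77 + 0.84) × 0.20 = 0.72 SD.

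**The case against.** The strongest reply is that these tests are openly exploratory. Moderation is not among the primary or secondary objectives in section 2. The trial has one primary outcome and one primary estimate, and the nine tests do not touch its type I error. The moderators and nearly all cut-points are fixed in advance; only usual SSB intake is split at the sample median. Unadjusted, prespecified exploratory interactions are common practice, and each test still has its own 5% error rate. All of this stands and lowers the severity. It does not remove the conflict between the exploratory heading and a rule that says moderation is present, with no caveat to settle which governs.

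The 37% assumes independence, and characteristics such as education, income and health literacy are probably correlated. This also stands, but the assumed correlations move the figure only to about 32% to 38%.

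Four stronger readings are tempting, and the documents do not support them:

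- **That familywise control is required.** For exploratory tests it is a choice, and step 5 shows that it would remove most of the little power there is.
- **That the plan treats a non-significant interaction as no moderation.** Section 6.3 never says so.
- **That non-significant β3 estimates will go unreported.** The text is silent on them. It promises subgroup effects for significant interactions and does not exclude the others.
- **That the same criticism covers the secondary outcomes.** The presence rule and the selective probing apply to the moderators alone, so this point does not extend to those outcomes.

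**Conclusion.** The point holds as a minor-to-moderate fault of wording and reporting. Followed as written, the rule has about a 37% chance of at least one false declaration when no characteristic moderates the effect and the tests are independent. The range is about 32% to 38% for latent correlations of 0 to 0.6 with age tested jointly, and about 37% to 44% if any single age term suffices. These ranges rest on assumed prevalences, correlations and outcome distribution; the independent-test figure needs only the nine tests and the 0.05 level.

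With about 29% power at an even split for an interaction as large as the whole planned effect, and less at uneven splits, interactions that pass are likely to be false or overstated. True interactions well above 0.283 SD would be the exception. A reader might infer that the trial's main conclusion is at risk; it is not, because the primary test is unaffected.

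**What to change.** Change the moderation paragraph of section 6.3 as follows:

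1. Replace the presence rule with a statement that nominally significant interactions are hypothesis-generating.
2. Report the interaction estimate, its 95% confidence interval and the arm effect in each subgroup for all nine moderators, significant or not.
3. State beside the results that nine interaction tests were done and that 0.45 would be expected to reach 0.05 by chance.
4. Test age with one joint interaction test on 3 df, and write Eq. 2 for that case with three interaction terms.

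Holm-adjusted p-values may be shown beside the nominal ones as an option, not as a required threshold.

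The cost is a revised paragraph, one extra table and less definite subgroup statements. No new data are needed, and the sample size and primary analysis do not change.
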